7.1.1 Treatment Administration

The study medications will be administered orally twice daily (every 12 hours, or BID) without regard to food. Note: For the 60 mg/day titration, this means 1 x 20 mg AERT in the morning and 2 x 20 mg AERT in the evening.

Once the subject has reached the maintenance dose, they will remain on that dose for approximately 1 year. The maintenance dose will be the highest tolerated dose, not exceeding 80 mg per day. All attempts should be made for subjects to titrate to the 80 mg per day dose. If subjects experience untoward tolerability issues due to AERT, they may taper study drug only under the guidance of the study site (i.e., in 20 mg increments per week). Subjects may subsequently attempt study drug taper if the investigator deems this clinically appropriate. There will be no taper phase for subjects who solely achieve a 40 mg per day maintenance dose. Subjects may attempt to titrate to the target dose of 80 mg per day, if tolerability issues have resolved.

If a subject misses 7 or more consecutive days of dosing AND has taken less than 80% of their doses of study medication in a 42-day (6-week) period, then the subject must be discontinued (see [Section 12.4](#)).

7.1.2 Labeling of Study Drug

Study medication will be provided in labeled bottles. The labels will include all information required by federal and local regulations.

7.1.3 Storage of Study Drug

Arbaclofen extended-release tablets must be stored at 20°C to 25°C (68°F to 77°F), excursions permitted to between 15°C and 30°C (59°F to 86°F) (see USP Controlled Room Temperature. At study sites, all study medication must be stored, secured, and locked in a safe place.

7.2 Study Drug Accountability

The Principal Investigator will have overall responsibility for the use of the study drug. The Principal Investigator or designee will confirm receipt of the study drug by signature and date. A copy of this receipt must be returned to the Sponsor or designee when the contents of the drug shipment have been verified. In addition, an accurate study drug dispensing record that specifies the date and amount dispensed to each subject must be kept in accordance with the study drug accountability form. This inventory record must be available for inspection during an audit (e.g., by Sponsor or a regulatory agency). At the conclusion of the study, the Principal Investigator must provide a copy of this record to the Sponsor.

Under no circumstances will the investigator allow the investigational drugs to be used other than as directed by this protocol. The study medication must be protected from unauthorized access (e.g., in a locked storage facility). Qualified study personnel must use the specified randomization system to assign subjects to treatment. Reasons for digression from the expected dispensing regimen must also be recorded.

At the end of the study, all medication must be reconciled. Any unused medication will be inventoried by the investigator or designee and retained by the site until instructed otherwise by Sponsor.

7.3 Handling and Disposal of Study Drug

The study drug must be protected from unauthorized access (e.g., in a locked storage facility).

Any unused, partially used, or empty bottles of study drug will be returned to the Sponsor or designee by the time of the site's close-out visit. Receipt, distribution, and return of the study drug must be properly documented on forms provided by the Sponsor or designee.

7.4 Method of Assignment of Study Drug

[figure not shown]
This is an open-label study and all subjects will begin treatment with AERT at 40 mg per day (20 mg BID) for 3 days, then increase to 60 mg per day (20 mg in the morning and 2 x 20 mg in the evening) for 3 days, and then increase to 80 mg per day (2 x 20 mg BID). Once the subject has reached the maintenance dose, they will remain on that dose for approximately 1 year. The maintenance dose will be the highest tolerated dose, not exceeding 80 mg per day. Subject will be allowed to taper the 80-mg/day dose for issues of tolerability on at most three occasions. If tolerability issues persist, the subject will be required to discontinue from the study.

After Baseline procedures have been completed, authorized site personnel will acknowledge that the applicable subject met all the specified inclusion criteria ([Section 5.1](#)) and none of the exclusion criteria ([Section 5.2](#)) and an enrollment number will be sequentially assigned.

7.5 Selection and Timing of Doses in the Study

There will be a 9-day titration period (3 days at 40 mg/day, 3 days at 60 mg/day, and 3 days at 80 mg/day), then a 1-year maintenance period, followed by a 2-week taper period. The maintenance dose will be the highest tolerated dose, not exceeding 80 mg per day. Subjects who discontinue early should also follow the 2-week taper period. Figure 2 presents the dosing regimen flowchart, including titration and taper, to be used during the study.

Figure 2: Flowchart of Open-Label Dosing Regimen, Study OS440-3005

At the end of treatment, a 2-week taper period will take place from Weeks 54 to 56. Subjects who discontinue early should also follow the 2-week taper period.

7.6 Emergency Unblinding

This is an open-label study.

7.7 Prior and Concomitant Therapy

The inclusion and exclusion criteria (Section 5.1 and 5.2, respectively) provide details on prohibited medications and food and the permitted duration since their last use prior to Baseline and/or study drug administration. For *de novo* subjects, all medications taken within 30 days before Baseline are to be recorded in the electronic case report form (eCRF). Eligible *de novo* subjects will undergo an up to 21-day washout period (no drug onboard) for withdrawal of all medications used for anti-spasticity and/or muscle relaxation prior to Baseline (see Inclusion Criterion 6). Any subject will be ineligible for the current open-label study if they are concomitantly using any of the medications listed in Appendix 5 (see Exclusion Criterion 5).

Table 3 presents the half-life, taper period, and washout period for specific anti-spasticity and/or muscle relaxation medications. Tapering of an existing anti-spasticity drug depends on the dose of the drug and other conditions. The investigator should use medical judgment to safely taper the dose. Under most conditions, the taper should take no more than 2 weeks. For anti-spasticity medications not shown in Table 3, please contact the medical monitor for discussions of the washout period.

Table 3: Taper and Washout Periods for Specific Anti-spasticity and/or Muscle Relaxation Medications, Study OS440-3005

Drug	Half-Life (hours)	Taper Period	Washout Period
Baclofen	3 to 5	3 to 14 days	1 day
Clonidine	12 to 16	3 to 14 days	3 days
Dantrolene	8 to 9	3 to 14 days	2 days
Gabapentin	5 to 7	3 to 14 days	2 days
Zanaflex	3	3 to 14 days	1 day
Diazepam	100	3 to 14 days	3 weeks

Other than anti-spasticity medications, all conventional medications regularly used for the treatment of MS and all non-pharmacological therapies (intended to alleviate spasticity, e.g., physiotherapy) are allowed provided they have been taken/administered for at least 1 month prior to enrollment and no dose adjustments are expected for the duration of this study.

Changes in either the dose or frequency of concomitant medications taken for the treatment of MS should not be made for the duration of this study. In the event a dose adjustment is needed for a concomitant medication, the investigator will contact the Sponsor to determine if the subject may remain in the study or needs to be withdrawn.

If a subject is receiving disease-modifying medications (especially interferons, see Inclusion Criterion 5), study visits should be scheduled prior to administration and, if possible, at a consistent time point during the study from when these drugs are administered in order to avoid interference with the temporary increase in spasticity that these medications may produce.

Subjects who experience an acute MS exacerbation/relapse (symptoms including but not limited to visual disturbance, dizziness, tingling, or extreme fatigue lasting greater than 24 hours and occurring at least 30 days after a previous relapse) requiring immediate therapy or adjustment in disease-modifying medication dose (e.g., oral or intravenous high-dose steroid therapy) will be discontinued from this study.

Other medication that is considered necessary for the subject's safety and well-being may be given at the discretion of the investigator. The administration of all medication (including investigational products) will be recorded in the appropriate sections of the eCRF.

Data collection for concomitant medications will include information on indication, dose, route, dosing frequency, start date, stop date, and will continue throughout the study.

The investigator or study staff will ask the subject at every study visit whether they have taken any new medications or had changes in their current medications since the last study visit. It is the responsibility of the investigator to ensure that any change in concomitant medications during the study is recorded in the source documentation and entered in the eCRF.

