5.1 Inclusion Criteria

Male and female subjects will be considered eligible for participation in the study if all the following inclusion criteria are satisfied at Visit 1 (Baseline).

1. Subjects 18 to 65 years of age, inclusive.
2. An established diagnosis per McDonald Criteria ([Polman et al 2011](#)) of MS (either RR or SP course) that manifests a documented history of spasticity for at least 6 months prior to Baseline.
3. Has participated in Study OS440-3004 or is a new US subject (i.e., a *de novo* subject) who fulfills the inclusion/exclusion criteria.
 - a. *De novo* subjects being considered for enrollment must have spasticity due to MS as shown by a TNmAS-MAL score $\geq 2^a$ (Appendix 1)
4. Is willing to continue on open-label treatment with AERT as described in this protocol.
5. If receiving disease-modifying medications (e.g., interferons approved for MS, glatiramer acetate, natalizumab, fingolimod, or mitoxantrone), there must be no change in dose for at least 3 months prior to Baseline, and the subject must be willing to maintain this treatment dose for the duration of the study. If receiving AMPYRA[®] (dalfampridine, fampridine, 4-amino puridine), subject must be at a stable dose for at least 3 months prior to Baseline.
6. Stable regimen for at least 1 month prior to Baseline for all medications and non-pharmacological therapies that are intended to alleviate spasticity.

^a Total numerical score of a limb accounts for the sum of the 3 main joint muscular group scores.

- a. *De novo* subjects being considered for enrollment and taking medications indicated for the treatment of spasticity (i.e., baclofen, benzodiazepines, cannabinoids, carisoprodol, dantrolene, tizanidine, cyclobenzaprine, any neuroleptic, ropinoprole, tolperisone, and clonidine) must wash out from these medications for at most 21 days by Baseline in order to be eligible for study treatment. *De novo* subjects found not to meet this criterion will be withdrawn from the study and will be considered screen failures.
7. Absence of infections, peripheral vascular disease, painful contractures, advanced arthritis, or other conditions that hinder evaluation of joint movement.
8. Creatinine clearance, as calculated by the glomerular filtration rate (GFR) using the Modification of Diet in Renal Disease Study (MDRD) formula,^b of >50 mL/minute.

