6.1 Screening – *De Novo* Subjects Only

For *de novo* subjects being considered for enrollment, a Screening visit (shown in Table 1) should occur a maximum of 21 days prior to Baseline to allow for any concomitant medication wash-out required for Inclusion Criterion 6. For *de novo* subjects, the following procedures will be done at this Screening visit:

- Obtain a signed and dated ICF from each subject prior to any study-specific procedures being conducted (Section 13.3).
- Assess eligibility according to the inclusion (Section 5.1) and exclusion criteria (Section 5.2).
- After establishing the subject's eligibility to participate, explain to *de novo* subjects how to withdraw all anti-spasticity medication (up to a 21-day period) prior to the next visit.
- Record demographic data, including age, sex, race, and ethnicity.
- Record medical and surgical history (Section 9.1).
- Record physical examination results (Section 9.3).
- Record weight and height (Section 9.4).
- Record vital sign measurements, including blood pressure (BP), heart rate, respiratory rate, and body temperature (Section 9.2).
- Collect blood and urine samples for hematology, serum chemistry, and urinalysis (Section 9.5). Subject should be fasting if possible.
- Perform a standard 12-lead electrocardiogram (ECG) (Section 9.6.1).
- Collect a sample to perform a serum pregnancy test (Section 7.8).
- Administer the Columbia–Suicide Severity Rating Scale (C-SSRS) (Section 9.6.3).
- Perform the TNmAS-MAL assessment (Section 8.2).
- Administer the EDSS assessment (Section 8.3).
- Administer the USP questionnaire (Section 9.6.2).
- Record all concomitant medications/therapies the subject is currently taking (Section 7.7).

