5. STUDY METHODS

5.1. General Study Design and Plan

As background for the statistical methods presented below, this section provides an overview of the study design and plan of study execution. The protocol is the definitive reference for all matters discussed in what follows.

This is a multicenter, open-label, long-term extension study to evaluate the safety and tolerability of oral AERT in subjects with spasticity due to MS. Subjects from the double-blind study (Study OS440-3004) may rollover into this open-label extension study, as well as de novo subjects, provided that all inclusion and none of the exclusion criteria are met.

Eligible de novo subjects will undergo an at least 21-day washout period for withdrawal of all medications used for anti-spasticity and/or muscle relaxation prior to enrolling in this open-label study. There will be a 9-day titration period, then a 52-week maintenance period, followed by a 2-week taper period.

[Figure 1](#) presents the timeline diagram for the study. [Figure 2](#) presents the open-label dosing regimen flowchart, including titration and taper doses, to be used during the study. Once the subject has reached the maintenance dose, they will remain on that dose for approximately 1 year. The maintenance dose will be the highest tolerated dose not exceeding 80 arbaclofen mg per day.

The schedule of assessments is presented in [Table 1](#).

Figure 1 **Timeline Diagram**

[figure not shown]
[figure not shown]

Figure 2 Flowchart of Open-Label Dosing Regimen

At the end of treatment, a 2-week taper period will take place from Weeks 54 to 56. Subjects who discontinue early should also follow the 2-week taper period.

Table 1 Schedule of Assessments

Assessment or Procedure	Baseline ¹	Visits							Final Visit ²
Study Visit	(V6 of prior DB Study)	1	2	3	4	5	6	7 (telephone visit)	8
Study Week	0 (±3 days)	2 (±3 days)	6 (±5 days)	14 (±5 days)	28 (±5 days)	42 (±5 days)	54 (±3 days)	56 (±5 days)	60 (±3 days)
Written informed consent	X								
Inclusion and exclusion criteria	X								
Withdrawal anti-spasticity medication	X								
Assign enrollment number	X								
Demography	X								
Medical/surgical history	X								
Physical examination	X								
Height	X								
Weight	X				X				X
Vital signs ³	X	X	X	X	X	X	X	X	X
Hematology/serum chemistry/urinalysis	X		X	X	X	X	X	X	X
Electrocardiogram	X				X				X
Pregnancy test ⁴	X	X	X	X	X	X	X	X	X
C-SSRS	X	X	X	X	X	X	X	X	X
TNmAS-MAL ⁵	X				X				X
EDSS	X				X				X
PGIC ⁶	X				X				X

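### For diazepam, the protocol's listed taper plus washout (24 to 35 days) does not fit the 21-day maximum from Screening to Baseline

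*Protocol*

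**What the plan says.** Protocol Section 7.7, Table 3, lists half-life, taper period and washout period for six drugs in separate columns. The diazepam row reads "Diazepam 100 3 to 14 days 3 weeks", with half-life in hours. The text above the table leaves the taper to medical judgment and adds: "Under most conditions, the taper should take no more than 2 weeks".

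The time allowed is stated in several places:

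- Section 5.1, Criterion 6a: de novo subjects on listed anti-spasticity drugs, benzodiazepines among them, "must wash out from these medications for at most 21 days by Baseline in order to be eligible for study treatment". Those "found not to meet this criterion will be withdrawn from the study and will be considered screen failures".
- Section 6.1: the Screening visit "should occur a maximum of 21 days prior to Baseline to allow for any concomitant medication wash-out required for Inclusion Criterion 6". At that visit, once eligibility is established, the site explains "how to withdraw all anti-spasticity medication (up to a 21-day period) prior to the next visit". A footnote to the protocol's Table 1 repeats the 21-day maximum.
- Section 7.7: eligible de novo subjects "will undergo an up to 21-day washout period (no drug onboard) for withdrawal of all medications used for anti-spasticity".

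SAP Section 5.1 differs: "Eligible de novo subjects will undergo an at least 21-day washout period".

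**The concern.** If withdrawal starts at Screening, both the taper and the washout must finish before Baseline. A 3-week washout uses the whole 21 days and leaves no room for a taper, yet Table 3 lists a taper of at least 3 days. A site with a diazepam user cannot follow both instructions.

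Two things are at stake. The first is eligibility: some subjects may be screen failures only because the figures do not fit. The second is consistency: a site that shortens the washout to meet the visit window could start AERT with some diazepam still present. That would bear on the Baseline TNmAS-MAL, which is the reference for change from baseline (SAP Section 9.2), and on adverse events in the titration period, which SAP Section 10.1 summarizes separately.

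**Working it through.** **Inputs.** Half-life 100 h, taper 3 to 14 days and washout 21 days for diazepam (Protocol Table 3). Maximum Screening-to-Baseline interval 21 days (Section 6.1 and Table 1 footnote). Baseline visit window ±3 days (Table 1).

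**Table 3's own washout figure.** The protocol gives no rule for its washout periods. Assuming five half-lives, 5 × 100 h = 500 h, and 500 / 24 = 20.8 days, or about 3 weeks. The diazepam entry is therefore consistent with its stated half-life as a drug-free period counted from the last dose.

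**Taper plus washout for each drug, in days.**

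| Drug | Shortest taper | Longest taper | Within 21? |
|---|---|---|---|
| Baclofen | 3 + 1 = 4 | 14 + 1 = 15 | Yes |
| Clonidine | 3 + 3 = 6 | 14 + 3 = 17 | Yes |
| Dantrolene | 3 + 2 = 5 | 14 + 2 = 16 | Yes |
| Gabapentin | 3 + 2 = 5 | 14 + 2 = 16 | Yes |
| Zanaflex | 3 + 1 = 4 | 14 + 1 = 15 | Yes |
| Diazepam | 3 + 21 = 24 | 14 + 21 = 35 | No |

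For diazepam the overrun is 24 − 21 = 3 days to 35 − 21 = 14 days.

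**Sensitivity to the visit window.** If the +3-day Baseline window could stretch the interval to 24 days, a 3-day taper would just fit (3 + 21 = 24). Any longer taper would not.

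**Drug-free time if the taper starts at Screening and Baseline falls on day 21.** This is 21 − 3 = 18 days after the shortest taper and 21 − 14 = 7 days after the longest.

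**Residual drug at Baseline.** Assuming first-order decay, the fraction of the level at the last dose is 0.5^(drug-free days × 24 / 100).

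- 18 days: 4.32 half-lives, 0.5^4.32 = 0.050, about 5%.
- 7 days: 1.68 half-lives, 0.5^1.68 = 0.312, about 31%.
- The full 21 days, for comparison: 5.04 half-lives, 0.5^5.04 = 0.030, about 3%.

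**Relative to the pre-taper level.** The level also falls during the taper. Assume a linear taper from steady state over T hours, with k = ln 2 / 100 per hour. The fraction left when the taper ends is then (1 − e^(−kT)) / (kT).

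- 14 days (T = 336, kT = 2.33): (1 − 0.097) / 2.33 = 0.39, and 0.39 × 0.312 = 0.12.
- 3 days (T = 72, kT = 0.499): (1 − 0.607) / 0.499 = 0.79, and 0.79 × 0.050 = 0.04.

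On that assumption about 12% and 4% of the pre-taper level would remain at Baseline.

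**The case against.** A reader might infer that diazepam users will reach Baseline with the drug still on board. The documents do not support that. Section 7.7 calls for no drug on board and makes anyone concomitantly using an Appendix 5 drug ineligible, and Appendix 5 includes benzodiazepines for an anti-spastic indication. Criterion 6a turns subjects who do not meet it into screen failures. On the plain reading the result is ineligibility, which costs recruitment and does not contaminate data. Residual drug remains only a possible outcome, because 6a states a ceiling and no minimum drug-free time: a site could taper for 14 days, leave 7 drug-free days and regard 6a as met.

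The 21-day limit in Criterion 6a and Section 7.7 can also be read as applying to the washout alone, in which case Table 3's 3 weeks equals the limit. That is fair for those two sections taken in isolation. It does not remove the conflict with Section 6.1, where withdrawal is explained at a visit no more than 21 days before Baseline. Nor can the washout column be read as including the taper, since other rows pair a taper of 3 to 14 days with a washout of 1 to 3 days. A taper begun before Screening would fit, but the protocol describes none.

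Two further inferences should be resisted. The 31% and 5% figures are fractions of the level at the last dose and must not be read as fractions of the pre-taper level. And nothing in the documents shows that residual diazepam would distort the Baseline USP score. The USP looks back over 4 weeks (Section 9.6.2), so even a complete 21-day washout leaves earlier treatment inside its recall period.

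The SAP's 21-day minimum is a separate matter. The SAP cites protocol version A01, names the protocol as the definitive reference, and itself gives a 21-day maximum in its Table 1 note. It needs correcting but adds nothing to the diazepam arithmetic. Finally, all analyses are descriptive (SAP Section 7.4.1), so no test result is at risk.

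**Conclusion.** The concern holds as an internal contradiction for one drug. Table 3 requires 24 to 35 days for diazepam and the visit schedule allows 21. De novo subjects taking diazepam for spasticity or muscle relaxation are either ineligible or 3 to 14 days short of the listed washout. The day counts rest on the documents alone, with withdrawal starting at Screening as Section 6.1 describes. The residual-drug percentages rest further on first-order decay and, for the pre-taper figures, on an assumed linear taper from steady state.

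The reach is small. Only US de novo subjects are concerned (SAP Section 6 mentions up to 50), and the documents do not say how many take diazepam. The practical harm is that sites may handle the same subject differently, with possible residual drug at the Baseline TNmAS-MAL and during early adverse-event collection in a few subjects.

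**What to change.** Reconcile Protocol Table 3, Section 7.7, Criterion 6a, Section 6.1 and the Table 1 footnote so that taper plus washout and the allowed window agree for every listed drug. Which taper, washout or window is right is for the sponsor's clinical team, and this review takes no view. Align SAP Section 5.1 with the current protocol and with the SAP's own Table 1 note.

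Optionally, add a derived flag in the SAP for de novo subjects whose recorded washout is shorter than the Table 3 figure. This needs no new data: Section 7.7 already collects medications taken within 30 days before Baseline, with stop dates, which covers a 21-day washout. These data will be listed anyway, so the flag only makes short washouts easier to find.

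The cost is a wording correction in each document and, if wanted, one derived variable.
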